10.2.5 Main analysis

- The tumour assessments will be derived according to the IWG treatment response criteria for malignant lymphoma (Cheson et al., 2007), by an Independent Radiology/Clinical Review Committee (IRC). The review process will be defined in the IRC Charter.
- The distribution of PFS will be estimated using the Kaplan-Meier (K-M) method. The median PFS time along with 95% confidence intervals will be presented (Brookmeyer and Crowley 1982). 25th and 75th percentiles will be considered as well.
- The PFS probabilities at specific time points (1 month, 3 months, 6 months, 12 months, 18 months, 24 months, 30 months), and the associated 95% CIs (Greenwood formula) will be summarized.
- PFS events will be described according to the type of event (death, documented tumour progression).
- The reason for censoring will be tabulated.
- A plot of the Kaplan-Meier curve for PFS will be provided.
- The median follow-up time for PFS including a 95% confidence interval (Brookmeyer and Crowley 1982) will be calculated using the reverse Kaplan-Meier method.
- No formal hypothesis testing will be conducted.
- The main analysis will be conducted on the FAS for both the IRC and INV response assessment.

10.2.6 Sensitivity analyses

- The main analysis as described in Section 10.2.5 will be conducted on the PPS.
- The main analysis as described in Section 10.2.5 will be conducted based on the INV response assessment as entered on the 'Lymphoma Tumour Assessment' eCRF page. The same censoring rules will apply as for the analysis based on the IRC assessment. If the response assessment is not based on radiological examination the date when the diagnosis of relapse or progression was made by the investigator is considered as the date of progression. The analysis will be conducted using both the FAS and the PPS.
- Patients having more than one missed visit, but having an available death date, will be included in the time-to-event analysis and considered as having a PFS event. The analysis will be performed on the FAS for both IRC and INV response assessment.

10.2.7 Concordance between IRC and INV assessment of PFS events

The concordance rate in terms of PFS events represents the agreement (PFS event, No PFS event) regarding the definition of these events based on the IRC and INV tumour response assessment, respectively. A contingency table will be generated and the concordance rate is calculated by adding the diagonal counts and dividing by the total number of patients. This concordance analysis will be performed on the FAS.

10.3 Secondary objective 3

10.3.1 Objective

To determine the duration of response (DoR).

10.3.2 Endpoint: Duration of response

DoR is defined as the elapsed time between the date of first documented response (CR or PR) and the following date of event defined as the first documented progression or death:

$\text{DoR [days]} = \text{date of assessment of tumour progression or death} - \text{date of assessment of first documented response of (CR or PR)} + 1.$

The DoR will be reported in months.

10.3.3 Censoring rules

14.1.1 Censoring situations

If a patient is alive and progression-free at the date of the analysis (i.e., at the cut-off date), the patient will be censored, and the reason for censoring will be provided as per Table 13.

15.1.1 Identification of two or more missing response assessments

If death or progression happens after two or more missed Tumour Assessments (TA), then the event is censored.

- An event occurring after two or more missing assessments or non-adequate tumour assessments will be censored on the date of last adequate tumour assessment.
- In one of the sensitivity analyses for PFS, an event occurring after two or more missing assessments is back-dated to the date of next scheduled assessment. The date of next scheduled assessment is the date of the last adequate tumour assessment plus the protocol specified time interval for assessments.
- If the patient has an EOT after two missed assessments without an event, then the patient will be censored for PFS at the last assessment and the censoring reason will be 'Adequate assessment no longer available'.

The maximum time [days] that can elapse between two response assessments without resulting in censoring is the same as for PFS and is shown in Table 14.

10.3.4 Main analysis

- The tumour assessments will be derived according to the IWG treatment response criteria for malignant lymphoma (Cheson et al., 2007), by an Independent Radiology/Clinical Review Committee (IRC). The review process will be defined in the IRC Charter.
- The distribution of DoR will be estimated using the Kaplan-Meier (K-M) method. The median DoR along with 95% confidence interval will be presented. 25th and 75th percentiles will also be shown.
- A plot of the Kaplan-Meier curve for DoR will be provided.
- The DoR probabilities at specific time points (1 month, 3 months, 6 months, 12 months, 18 months, 24 months, 30 months), and the associated 95% CIs (Greenwood formula) will be summarized.
- No formal hypothesis testing will be conducted.
- The main analysis will be conducted on the FAS based on the IRC response assessment.

10.3.5 Sensitivity analyses

- The main analysis as described in Section 10.3.4 will be conducted based on the INV response assessment as entered on the 'Lymphoma Tumour Assessment' eCRF page. The same censoring rules will apply as for the analysis based on the IRC assessment. The analysis will be conducted using the FAS.
- DoR stratified by best overall response: The DoR will be stratified by patients who reached PR as best overall response, and patients who reached CR as best overall response:
 - The stratified DoR will be tabulated according to both INV and IRC response assessment (for the FAS):
 - Kaplan-Meier methods will be used to derive median, Q1, Q3, and 95% confidence intervals (for the FAS).
 - Kaplan-Meier curves will be presented. The graph will include the following strata: DoR for patients with PR as best response, CR as best response, and one group representing the DoR for all responders (for the FAS).

- Duration of CR:

The duration of CR (in days) is defined as follows: (date of assessment of tumour progression or death – date of assessment of tumour response [CR] + 1). The duration of CR will be reported in months and tabulated according to both local and IRC radiological assessments. The duration of CR will be analysed using Kaplan-Meier methods (median, Q1, Q3, 95% confidence intervals). A Kaplan-Meier curve will be shown. The analysis will be performed on the FAS for both IRC and INV response assessment.

10.4 Secondary objective 4

10.4.1 Objective

To determine the overall survival (OS).

10.4.2 Endpoint: Overall survival

Overall survival (OS) is defined as the time from the date of the first administration of any study drug until death from any cause (documented by the date of death).

10.4.3 Censoring rules and imputation

Patients who are alive or who drop out early for any reason will be censored at date of last contact.

If for a patient's death month and year are provided but the day is missing, the day will set to the first day of the month, unless other qualifying study data support survival until a later date during the same month. If day and month or year is missing, no imputation will be done and the date of death will be censored at the date of last contact. A listing showing the information on eCRF pages for survival follow-up and end of survival follow-up will be presented (for the SAF).

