10.6.2.2 Duration of Response (DoR) and Time to Next Treatment (TTNT)

DoR is defined as the time interval between the initial time point of tumour response (CR or PR whichever status is recorded first) and the first date that recurrence of progressive disease is documented. Response duration by the local and central assessment will be tabulated with descriptive statistics.

Disease progression is defined as the first occurrence of progressive disease according to the revised response criteria ([Cheson et al., 2007](#)) as assessed by central radiology / clinical readers.

TTNT is defined as the time from study entry (= first dosing) to the institution of next therapy for any reason including disease progression, treatment toxicity and patient preference. TTNT will be descriptively analysed.

10.6.2.3 Time to Event Variables: Progression-Free Survival (PFS), Overall Survival (OS), and Time to Progression (TTP)

PFS is defined as the time elapsed between study entry (= first dosing) and lymphoma progression or death from any cause, whichever occurs first. Patients not experiencing a lymphoma progression or death from any cause will be censored at the last available tumour assessment. The same holds true for patients who are lost-to-follow-up.

OS is defined as time from study entry (= first dosing) until the date of death from any cause. Patients who are alive but have dropped out early will be censored at the time of the last available study visit assessment.

TTP is defined as the time from study entry (= first dosing) until documented lymphoma progression or death as a result of lymphoma. The events of interest are only disease progression and death from lymphoma. Death from other causes will not be taken into account (will be censored) in the TTP evaluation. Patients not experiencing progressive disease will be censored at the last NHL assessment. Deaths from other causes will be censored at the time of death. Early drop-outs without any documented date of progression will be censored at the time of the last NHL assessment.

Kaplan-Meier methodology will be used to evaluate median survival, presenting corresponding statistical parameters and Kaplan-Meier survival curves. Further analyses concerning influence of IPI and GC/non-GC B-cells will be specified in the SAP.

TTP will be compared to the TTP of the patients' most recent therapy by tabulating descriptive statistics (including 95% confidence limits).

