6.10 Date of last contact

The date of last contact is derived for patients not known to have died at the analysis cut-off date (see section 7.4) based on the latest date among the following:

- Actual assessment dates (Labs, vital signs, performance status, tumour imaging, EOT completion, PK sample collection dates).
- Antineoplastic therapies administered after study drug discontinuation.
- Adverse events dates.
- “Date of contact” or “Last known date patient alive” collected on the “Survival Follow-up” eCRF page (if applicable).
- Date of study completion or discontinuation from the “End of Survival Follow-up” eCRF page.
- Study treatment start/end date.

The date of last contact is defined as the latest date from the above list or the cut-off date whichever comes first. In case that a date is only partially complete the following rules will be applied. If month and year are present and only the day is missing the first day of the month will be used to impute the missing date. If day and month or year is missing the date will not be imputed. The date of last contact is used for censoring of patients in the analysis of overall survival and time to next treatment.

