10.4.4 Main analysis

- The distribution of OS will be estimated using the Kaplan-Meier (K-M) method. The median OS time along with 95% confidence intervals will be presented (Brookmeyer and Crowley 1982). 25th and 75th percentiles will be considered as well.
- The OS probabilities at specific time points (1 month, 3 months, 6 months, 12 months, 18 months, 24 months, 36 months, 48 months), and the associate 95% CIs (Greenwood formula) will be summarized.
- A plot of the Kaplan-Meier curve for OS will be provided.
- The median follow-up for OS will be calculated using the reverse Kaplan-Meier method.
- No formal hypothesis testing will be conducted.
- The main analysis will be conducted on the FAS.

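### A patient known to have died is censored in the overall survival analysis when the day and month, or the year, of death are missing

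*SAP*

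**What the plan says.** SAP 10.4.2 gives the OS definition: "time from the date of the first administration of any study drug until death from any cause (documented by the date of death"). SAP 10.4.4 adds: "The distribution of OS will be estimated using the Kaplan-Meier (K-M) method".

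SAP 10.4.3 treats incomplete death dates in two ways:

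- **Month and year known, day missing:** the death is dated to the 1st, or later if other data show the patient alive after that. The patient stays an event.
- **More than the day missing:** "no imputation will be done and the date of death will be censored at the date of last contact". The patient becomes a censored observation.

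SAP 6.10 defines the censoring date: "The date of last contact is derived for patients not known to have died at the analysis cut-off date".

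Protocol 10.6.2.3 gives the OS censoring rule as: "Patients who are alive but have dropped out early will be censored at the time of the last available study visit assessment". It mentions no censoring of patients who have died.

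**The concern.** For these patients the event is certain and only its date is imprecise. Kaplan-Meier estimation treats a censored patient as still alive at the censoring date, with the same outlook as those who remain at risk. Here the patient is censored because a death was recorded, so the censoring is informative by construction and always works in the same direction.

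At stake are the OS median and the OS rates at the time points in SAP 10.4.4, which run to 48 months. The subgroup OS rates in the addenda are also affected, and there one lost death weighs more because fewer patients are at risk.

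**Working it through.** **1. The rule against the other passages**

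| Passage | What it implies for a known death with only the year recorded |
|---|---|
| SAP 10.4.2 | An event, since OS runs "until death from any cause" |
| Protocol 10.6.2.3 | Not among those censored, who are alive |
| SAP 10.4.3, day missing | Imputed and kept as an event |
| SAP 10.4.3, day and month missing | Censored at last contact |
| SAP 6.10 | No date of last contact is derived once the patient is known to have died by the cut-off |
| SAP 10.4.5 | Repeats the analysis on the per-protocol set under the same date rule |
| SAP 20.8.1 | Repeats OS on the safety set by reference to Section 10.4 |
| SAP 20.9 | Alternative censoring for PFS and DoR only |

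The phrase listing the missing date parts can be parsed in two ways, but a death with only the year known is covered on either reading. If the list in SAP 6.10 were applied to a patient who has died, it could return the contact at which the death was reported, because contact dates and the end-of-follow-up date are on that list.

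**2. Direction and size for one patient**

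The documents state no OS event count, target or power, so there is no planned figure to reproduce. Suppose a patient is censored when n are at risk, and nobody else is censored before the true date of death. From that date on,

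S(with rule) = S(correct) × n/(n − 1), an increase of S/(n − 1).

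Hand check with 80 patients and S = 0.50 at 24 months, so 40 deaths by then:

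- For a death with 80 at risk: 0.50/79 = 0.63 points.
- For a death with 41 at risk: 0.50/40 = 1.25 points.
- Mean over the 40 deaths: 0.50 × (1/40 + 1/41 + … + 1/79)/40 = 0.50 × 0.699/40 = 0.87 points.
- With about 66 deaths over 60 months, the chance that the affected death falls before 24 months is 40/66 = 0.61, and 0.61 × 0.87 = 0.53 points.

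**3. Simulation**

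Inputs from the documents: about 80 patients (SAP 5.3); 60 months of follow-up and 90-day contacts (Protocol 7.2.5); and a median OS of 10.7 months, quoted in Protocol 1.3.3 for a lenalidomide plus rituximab study.

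Assumptions: exponential survival; median OS of 24 and 36 months as further values; last contact 0 to 90 days before death; 1, 2, 4 or 8 affected deaths picked at random. There were 3,000 runs per scenario, each compared with the same data with every death kept as an event. Runs without a finite shift in the median were left out of that column.

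| Affected deaths | Rise in 24-month OS (points) | Rise in 48-month OS (points) | Rise in median OS (months) |
|---|---|---|---|
| 0 | 0 | 0 | 0 |
| 1 | 0.4 to 0.5 | 0.2 to 0.6 | 0.2 to 1.0 |
| 2 | 0.8 to 1.0 | 0.3 to 1.3 | 0.4 to 1.9 |
| 4 | 1.6 to 2.1 | 0.7 to 2.7 | 0.7 to 3.5 |
| 8 | 3.3 to 4.3 | 1.5 to 5.5 | 1.3 to 6.7 |

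Ranges run over the three medians. At a median of 24 months the simulated rise in 24-month OS for one death is 0.50 points, against 0.53 by hand. The hand figure ignores the gap between last contact and death, which makes n larger.

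**The case against.** The strongest defence is that the rule will seldom apply and will move little when it does. Calls are due every 90 days, patients lost to follow-up get at least three documented contact attempts (Protocol 7.2.5), and deaths can be confirmed from public records (SAP 6.13.9 and 7.4). A wholly unknown month should therefore be rare, and zero is a plausible count. OS is a descriptive secondary endpoint without hypothesis testing. With 80 patients and survival near 50%, the 95% interval half-width is about 1.96 × √(0.25/80) = 11 points, far more than the shift from one or two deaths. The affected deaths also stay in the death listing and summaries under SAP 10.7.3, so they can be traced. All of this stands and sets the severity, but it does not justify the rule.

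The conflict with SAP 6.10 also has a limit. If the year is missing, or the cut-off falls within the known year, the date field alone does not show that death preceded the cut-off. The conflict is plain where the known year ended before the cut-off or the report itself predates it.

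A reader might infer two stronger points that the documents do not support:

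- **PFS and time to next treatment are biased in the same way.** The rule stands under OS only. PFS has its own censoring table (SAP 10.2.4), and SAP 20.9 notes that PFS follow-up stops with treatment. SAP 10.6.2 counts death as an event for time to next treatment but gives no rule for partial death dates, and silence is not the same rule.
- **The losses cluster late, in deaths reported by relatives by phone.** No passage links missing months to phone reports. Phone follow-up begins after the 30-day visit, so a patient who stops early enters it early, and such deaths could fall anywhere on the curve.

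**Conclusion.** The stated rule is wrong for OS. Followed exactly, it removes a certain event, conflicts with the SAP's own endpoint and with the protocol, and calls for a date the SAP does not define for these patients. From the true date of death onwards it can only raise the estimated curve.

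The likely effect is small: about 0.4 to 0.5 points in 24-month OS per affected death among 80 patients, and nothing if there are none. That figure rests on the assumed survival distribution, the assumed medians and an assumed count. The documents give no number of deaths with incomplete dates. Severity is minor.

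**What to change.** Replace the last rule in SAP 10.4.3. When death is known to have occurred on or before the cut-off, count it as an OS event and date it by a pre-specified rule, for example the midpoint, within this interval:

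- **Start:** the last date known alive, or 1 January of the known year if that is later.
- **End:** the earliest of the date the death was reported, 31 December of the known year, and the cut-off.
- **Year missing:** the same interval without the year bounds.

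The report date is needed. Take a patient last known alive on 1 February of a non-leap year whose death is reported on 5 May with only the year given. Without the report date, the midpoint of the 333 days to 31 December is about 17 July, after the site already knew of the death. With it, the midpoint of the 93 days is about 19 March.

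Extend SAP 6.10 so that a last-known-alive date is also derived for patients who have died. Report the number of deaths dated in this way, and add an OS sensitivity analysis at the earliest and latest possible dates.

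The cost is one derivation rule and a little programming. OS may come out slightly lower.

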10.4.4 Main analysis

- The distribution of OS will be estimated using the Kaplan-Meier (K-M) method. The median OS time along with 95% confidence intervals will be presented (Brookmeyer and Crowley 1982). 25th and 75th percentiles will be considered as well.
- The OS probabilities at specific time points (1 month, 3 months, 6 months, 12 months, 18 months, 24 months, 36 months, 48 months), and the associate 95% CIs (Greenwood formula) will be summarized.
- A plot of the Kaplan-Meier curve for OS will be provided.
- The median follow-up for OS will be calculated using the reverse Kaplan-Meier method.
- No formal hypothesis testing will be conducted.
- The main analysis will be conducted on the FAS.

10.4.5 Sensitivity analyses

- The main analysis as described in Section 10.4.4 will be conducted on the PPS.

10.5 Secondary objective 5 and secondary objective 11

10.5.1 Objectives

- Objective 5: To determine the time to progression (TTP).
- Objective 11: To compare each patient's TTP on LEN plus MOR00208 with the TTP of their most recent prior therapy.

10.5.2 Endpoint: Time to progression

TTP is defined as the time from the first administration of any study drug until documented DLBCL progression or death as a result of lymphoma. Death from other causes than lymphoma will not be considered in relation to the TTP evaluation.

If a patient does not have an event, TTP will be censored on the date of the last tumour assessment before the data analysis cut-off date or the anti-neoplastic therapy start date if the patient started any new anti-neoplastic therapy or the date of death for death from other causes than lymphoma.

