**Table 13: Censoring Rules**

Situation	Date of Progression or Censoring	Outcome	Censoring reason
Ongoing and No event until data cut-off	Date of last adequate tumour assessment	Censored	Ongoing
Discontinued the study with no event	Date of last adequate tumour assessment	Censored	Discontinued without event
No baseline tumour assessment	Date of C1D1	Censored	No baseline tumour assessment
Lost to follow-up	Date of last IRC tumour assessment (or C1D1 in case of study discontinuation w/o progression before any post-baseline assessment)	Censored	Lost to follow-up
Patient received non-study anti-DLBCL treatment before disease progression	Date of last adequate tumour assessment before start of non-study cancer treatment	Censored	New anti-cancer therapy started
Clinical Progression*	Date of last adequate tumour assessment	Censored for Analysis based on Investigator assessment only	Clinical Progression not validated by Cheson Criteria
PD by modality not including PET Scan is not confirmed by modality including PET Scan**.	Date of last adequate tumour assessment	Censored for Analysis based on Investigator assessment only	Non-PET PD not confirmed by PET.
Death before any date of PD assessment	Date of death	Progressed	
Death between adequate assessments	Date of death	Progressed	
Death or progression after two or more	Date of last adequate	Censored	Event documented

STATISTICAL ANALYSIS PLAN

 MorphoSys AG
 MOR208C203

Situation	Date of Progression or Censoring	Outcome	Censoring reason
missed visits	tumour assessment		after two or more missing tumor assessments
EOT after two or more missed assessments without disease progression	Date of Last adequate Tumour Assessment	Censored	Adequate assessment no longer available

Abbreviations: EOT = End of Treatment; IRC = Independent Review Committee; PD = progressive disease; CT = Computed tomography; PET = Positron emission tomography. *Progression as per Investigator's assessment and without meeting PD criteria according to Response Criteria for Malignant Lymphoma (Cheson et al., 2007). **The rule only applies in case a PET-including modality is performed after a non-PET including modality.

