10.5.3 Main analyses

16.1.1 Main analysis for Objective 5

- The tumour assessments will be derived according to the IWG treatment response criteria for malignant lymphoma (Cheson et al., 2007), by an Independent Radiology/Clinical Review Committee (IRC). The review process will be defined in the IRC Charter.
- The distribution of TTP will be estimated using the Kaplan-Meier (K-M) method. The median TTP along with 95% confidence intervals will be presented (Brookmeyer and Crowley 1982). 25th and 75th percentiles will be considered as well.
- The TTP probabilities at specific time points (1 month, 3 months, 6 months, 12 months, 18 months, 24 months), and the associate 95% CIs (Greenwood formula) will be summarized.
- TTP events will be described according to the type of events (death due to lymphoma, documented tumour progression).
- A plot of the Kaplan-Meier curve for TTP will be provided.
- No formal hypothesis testing will be conducted.

17.1.1 Analysis for Objective 11

TTP will be compared with TTP of each patient's most recent therapy via tabulating descriptive statistics for TTP of patient's most recent therapy. A graph showing the Kaplan- Meier curve for patients' last prior treatment will be generated for the FAS.

The following therapies will be considered as most recent therapy:

- Last prior systemic anti-DLBCL medication (taken from the eCRF page: Prior Cancer Therapies for DLBCL-Medications)
- ASCT in case the last prior treatment was ASCT (taken from the eCRF page: Prior Cancer Therapies for DLBCL-Autologous Stem Cell Transplants)

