20.9 PFS and DoR analyses applying alternative censoring rules

Analyses for the endpoints PFS and DoR will be performed using alternative censoring rules, i.e., three scenarios that led to censoring as per Table 13 will be considered as a PFS event.

Situation	Outcome as per main analysis (see Table 13)	Censoring date as per main analysis (see Table 13)	Outcome as per alternative censoring rules	Date of progression as per alternative censoring rules
Discontinued the	Censored	Date of last	Event	Date of

STATISTICAL ANALYSIS PLAN

 MorphoSys AG
 MOR208C203

Situation	Outcome as per main analysis (see Table 13)	Censoring date as per main analysis (see Table 13)	Outcome as per alternative censoring rules	Date of progression as per alternative censoring rules
study with no event		adequate tumour assessment		discontinuation of the study drug that was discontinued latest*
Patient received non-study anti-DLBCL treatment before disease progression	Censored	Date of last adequate tumour assessment before start of non-study cancer treatment	Event	Date of initiation of non-study anti-DLBCL treatment
Death or progression after two or more missed visits	Censored	Date of last adequate tumour assessment	Event	Date of the first missed tumour assessment (i.e., the planned date of the assessment that was missed)

*Note: in L-MIND, PFS follow-up stops with treatment discontinuation (a post-treatment PFS follow-up is not conducted in L-MIND).

The censoring strategy for the remaining scenarios described in Table 13 will still apply.

The following analyses applying the alternative censoring rules will be conducted:

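### As worded, the TTP rule counts lymphoma deaths after non-study treatment as events but takes comparable survivors out at or before the start of that treatment

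*SAP*

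**What the plan says.** **Event.** SAP 10.5.2 runs TTP from first dose "until documented DLBCL progression or death as a result of lymphoma". It does not exclude events that follow new anti-neoplastic therapy.

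**Censoring.** One sentence in the same section covers it. It opens "If a patient does not have an event, TTP will be censored on the date of the last tumour assessment" before the data cut-off, and adds two alternatives joined by *or*: "the anti-neoplastic therapy start date if the patient started any new anti-neoplastic therapy", and "the date of death for death from other causes than lymphoma". No order of precedence is given.

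**Estimator.** SAP 10.5.3: "The distribution of TTP will be estimated using the Kaplan-Meier (K-M) method". The main analysis uses the independent review (IRC).

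**PFS and DoR.** For non-study treatment before progression, Table 13 sets the PFS censoring date as "Date of last adequate tumour assessment before start of non-study cancer treatment". SAP 10.3.3 refers DoR to the same table. The TTP section does not refer to it.

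**Protocol.** Section 10.6.2.3 has no new-therapy rule for TTP: "Patients not experiencing progressive disease will be censored at the last NHL assessment". Deaths from other causes are censored at death.

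**Follow-up.** A note in SAP 20.9 says that "PFS follow-up stops with treatment discontinuation". Deaths continue to be collected: SAP 6.9 accepts dates from survival follow-up, and protocol 8.2 has lymphoma deaths recorded in that period.

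**The concern.** Kaplan-Meier needs a patient's presence in the risk set at a given time to be settled without knowing what happens to that patient later. The literal rule breaks this. Time after the switch counts for patients who go on to die of lymphoma and is discarded for those who do not. Tumour follow-up stops with study treatment, so events after a switch are almost only lymphoma deaths.

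Three things are at stake:

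- TTP is secondary objective 5 and supplies the study side of the within-patient comparison in objective 11. It also feeds the IPI strata (SAP 10.10) and the centrally confirmed DLBCL subgroup (SAP 20.6.1).
- TTP could contain lymphoma deaths that PFS censors, although PFS counts death from any cause.
- Censoring at therapy start, where that reading is used, departs from the protocol's last-assessment rule and credits unassessed time as progression-free.

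**Working it through.** The plan gives no TTP event count, rate or power, so there is no figure of its own to reproduce. The check is a comparison of the rules, followed by an illustration of size.

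**1. Same patient, different rules.** Let a patient start non-study treatment at time *a* without counted progression. The last adequate scan was at *s* ≤ *a*, and cut-off is at *c*.

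| Later course | SAP 10.5.2, literal | Table 13 (PFS, DoR) |
|---|---|---|
| Lymphoma death at *d* < *c* | Event at *d* | Censored at *s* |
| Alive at *c* | Censored at *a* or *s*, depending on parsing | Censored at *s* |
| Death from another cause after *a* | Censored at *a*, *s* or the death date; no precedence | Censored at *s* |

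Kaplan-Meier is S(t) = ∏(1 − dᵢ/Yᵢ). For event times after *a*, the literal rule keeps switchers in Yᵢ only if they will later contribute to dᵢ. The late hazard is therefore overstated.

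**2. Are there such patients?** The SAP expects some. Section 8.7.6 tabulates non-study treatment without documented radiological progression, and Section 20.4.1 has a subgroup censored for PFS that received later anti-DLBCL medication. No number is given. IRC progression before the switch is already an event, so those patients are not affected.

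**3. Size at an assumed true 24-month rate of 25%.** All inputs are assumptions:

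- exponential TTP, median 12 months: λ = ln 2/12 = 0.0578 per month, so S(24) = exp(−24λ) = 0.25;
- switching independent of prognosis, hazard λ·q/(1 − q) with q = 0.1, 0.2, 0.3, giving about 9%, 18% and 27% who switch before progression;
- exponential time from switch to lymphoma death, median 6, 12, 24 or 48 months;
- cut-off uniform on 12 to 60 months; 200,000 patients per scenario.

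Kaplan-Meier at 24 months, literal rule / everyone censored at the switch:

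| Median from switch to lymphoma death | about 9% switch | about 18% | about 27% |
|---|---|---|---|
| 6 months | 0.230 / 0.250 | 0.209 / 0.252 | 0.184 / 0.251 |
| 12 months | 0.241 / 0.250 | 0.230 / 0.250 | 0.217 / 0.250 |
| 24 months | 0.247 / 0.249 | 0.245 / 0.250 | 0.241 / 0.249 |
| 48 months | 0.250 / 0.250 | 0.251 / 0.250 | 0.251 / 0.250 |

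The largest gaps are 2.0, 4.3 and 6.7 points; the smallest are zero within simulation error. The median is 10.7 to 12.1 months under the literal rule and 11.9 to 12.0 under uniform censoring.

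A third rule follows every switcher to lymphoma death or cut-off. It has the same events as the literal rule and differs only in how long survivors stay at risk. The literal estimate was below it in every scenario, by 0.3 to 9.4 points. That isolates the direction of the defect, although following through answers a different question because it includes the effect of the next treatment.

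**4. A higher assumed rate.** With a true 24-month rate of 50%, switches spread over months 1 to 12 and cut-off at 24 to 48 months, the literal rule gave:

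| Patients switching | Median to death 6–12 months | Median to death 24–48 months |
|---|---|---|
| about 8% | 45.8 to 47.3% | 48.6 to 49.3% |
| about 25% | 38.0 to 41.8% | 45.1 to 47.3% |

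The gap at 25% switching is thus 50 − 41.8 = 8.2 to 50 − 38.0 = 12.0 points when deaths are fast, and 2.7 to 4.9 points when they are slow.

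**5. If missed-assessment censoring applies.** With the Table 14 windows imposed, a true rate of 50% and a 6-month median to death, 45.8% becomes 47.5 to 47.9% (8% switching), 41.9% becomes 45.1 to 46.0% (17%), and 37.9% becomes 42.3 to 43.6% (25%). The gap roughly halves and does not vanish: the shortest window is 114 days, so earlier deaths still count.

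**The case against.** **The sentence can be parsed another way.** Cut-off and therapy start could be two parallel limits, with the absence of an event judged before whichever comes first. That is the usual convention and would match Table 13 on which events count. The reading is possible, but it is not what the condition says, and the event definition has no such limit. A programmer could implement either reading.

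**SAP 10.5.4 narrows the problem.** One TTP sensitivity analysis counts patients lost to follow-up, or with an event after more than one missed visit, as events when a death date is available. That differs from the main analysis only if the main analysis censors them. Many late lymphoma deaths would then drop out. This stands as a limit on size. It is an inference, because 10.5.2 states no such rule, and early deaths would remain.

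**The size is uncertain.** The documents give no switch rate, and protocol 6.7 bars other antineoplastic therapy before progression during treatment. The gap to uniform censoring depends heavily on how soon deaths follow the switch. This stands.

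**Uniform censoring is not free of bias.** It recovers the assumed curve because switching was simulated as unrelated to prognosis. Table 13 itself has a category for clinical progression that does not meet the Cheson criteria. Patients who switch for that reason have a worse outlook, and censoring them would overstate TTP. This stands.

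**Other analyses cover new therapy.** PFS, its alternative censoring (SAP 20.9), EFS (16.4.2) and TTNT (10.6) all do. They limit reliance on TTP but do not repair it.

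**Conclusion.** The concern holds for the literal wording of SAP 10.5.2. Whether a switcher's later time counts depends on whether that patient later dies of lymphoma. The effect tends to shorten TTP, and the rule is inconsistent with PFS and DoR.

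Three stronger readings are tempting and are not supported:

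- *A material bias in this trial has been shown.* The documents do not give the number of switchers or the timing of their deaths. At an assumed true rate of 25% the illustrated gap to uniform censoring runs from about 0 to 7 points. It is larger at 50%, and smaller if the missed-assessment rule applies.
- *Every patient without an event leaves no later than the switch.* A patient who switches and dies of another cause may be censored at death, because the three dates have no precedence.
- *Uniform censoring gives the true TTP.* It does so only if switching is unrelated to prognosis. What it does remove is the dependence on later outcome.

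TTP is secondary and descriptive, with no hypothesis test, and objective 11 is a tabulation. ORR, PFS, DoR and OS are unaffected. The wording should be corrected, but no principal result depends on it.

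**What to change.** Replace the censoring sentence in SAP 10.5.2 with rules to this effect:

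1. A patient who starts non-study anti-DLBCL treatment before documented progression is censored at the last adequate tumour assessment before that start, whatever is recorded later, as in Table 13.
2. Only progression or lymphoma death before such treatment is a TTP event.
3. Death from another cause before such treatment is censored at the date of death, as in protocol 10.6.2.3.
4. State whether the missed-assessment rule of Tables 13 and 14 applies to the main TTP analysis, so that the sensitivity analysis in 10.5.4 has a defined contrast.

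Add a note that this censoring may still be informative when a switch follows clinical worsening. A supplementary TTP that counts the start of new treatment as an event, as SAP 16.4.2 does for EFS, is optional.

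The cost is a wording change and one revised derivation, using dates already derived for PFS. No new data are needed.
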